6.12.7 Pulmonary Function Tests

At the study Visits 1 and 17 (Screening and study Week 32) pulmonary function tests (PFTs) will be performed, including assessment of FEV₁ and FVC. Spirometry will be performed in accordance with American Thoracic Society standards. The results will be compared to the predicted values based on factors such as age, gender, and ethnicity to the lower level of normal (LLN).

Additional pulmonary assessments will be done in case of clinically significant abnormal findings on the PFTs or physical examination and at the discretion of the Investigator in subjects with respiratory complaints like dyspnea, shortness of breath, chest tightness, wheezing etc.

Spirometry parameters such as FEV₁, FEV₁ Percent Predicted, FVC, FVC Percent Predicted and FEV₁/FVC Ratio as well as their changes from baseline to Week 32 will be summarized descriptively by visit.

6.12.8 Ophthalmological Examination

[figure not shown]
At the study Visits 1, 9 and 17 (Screening and study Weeks 12 and 32) a complete ophthalmologic examination will be performed by an ophthalmologist, including an ophthalmological history, best corrected visual acuity (Snellen chart), ophthalmoscopy (preferably slit-lamp) and Optical Coherence Tomography (OCT) assessment (measurement of central foveal thickness).

The following results of the ophthalmological examination will be summarized descriptively by eye (left or right), visit and treatment group:

- Best corrected visual acuity (Snellen denominator)
- OCT results: central fovea thickness

Number and percentage of subjects with presence of macular edema and/or uveitis will be presented by visit and overall across all visits (including both scheduled and unscheduled visits).

All ophthalmological examination data will be listed.

Number and percentage of subjects requiring monitoring beyond 6 hours will be provided along with reasons, treatment group and visit as well as overall across all visits.

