Title of Study: A RANDOMIZED, DOUBLE-BLIND, PLACEBO-CONTROLLED STUDY TO ASSESS THE EFFICACY AND SAFETY OF SCD-044 IN THE TREATMENT OF MODERATE TO SEVERE ATOPIC DERMATITIS

Sponsor: Sun Pharmaceutical Industries Ltd

[REDACTED]

[REDACTED]

[REDACTED]

Start of the study: in North and Latin America: June 2021 [first participant enrolled]
in Europe: July 2023 [anticipated open for recruitment]

End of the study: the study is expected to be concluded upon final collection of data for all outcome measures and adverse events, including safety follow up (last participant's last visit).

Investigational Products: SCD-044 Tablets [REDACTED] (Low dose)
SCD-044 Tablets [REDACTED] (Intermediate dose)
SCD-044 Tablets [REDACTED] (High dose)
SCD-044 Tablets [REDACTED])

Control: Placebo of SCD-044 product

Treatment Duration: The study treatment period will last up to 32 weeks

Dose and Mode of Administration: [REDACTED] according to a randomization scheme and [REDACTED] schedule.

Objectives:

Primary Objective:

- To determine the effect of SCD-044 treatment on moderate to severe atopic dermatitis, as measured by proportion of subjects showing at least 75% improvement in Eczema Area and Severity Index (EASI) at Week 16.

Secondary Objectives:

- To evaluate the efficacy of SCD-044 as measured by validated Investigator's Global Assessment (vIGA) of disease severity
- To evaluate the efficacy of SCD-044 as measured by Peak Pruritus Numeric Rating Scale (PP-NRS)
- To evaluate the efficacy of SCD-044 as measured by SCORing Atopic Dermatitis (SCORAD)
- To evaluate the efficacy of SCD-044 as measured by Patient Oriented Eczema Measure (POEM)
- To evaluate the efficacy of SCD-044 as measured by change in body surface area (BSA) involvement over the treatment period
- To assess the effect of SCD-044 on quality of life, as measured by Dermatology Life Quality Index (DLQI)
- To assess the effect of SCD-044 on Patient Global Impression of Severity (PGIS)
- To assess the effect of SCD-044 on Patient Global Impression of Change (PGIC)
- To assess the safety and tolerability of SCD-044 in subjects with moderate to severe atopic dermatitis

[REDACTED]
[REDACTED]
[REDACTED]
[REDACTED]

Design:

Subjects in this randomized, double-blind, placebo controlled, parallel-group, multiple-center study will be assigned to treatment with the investigational products or placebo control according to a randomization scheme and [REDACTED] schedule:

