4. STUDY POPULATION

4.1 Number of Subjects

Approximately 240 subjects will be enrolled in the study in a [REDACTED] the following treatment groups:

- Placebo of SCD-044 product [REDACTED]
- SCD-044 Tablets (Low dose)
- SCD-044 Tablets (Intermediate dose)
- SCD-044 Tablets (High dose)

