6. STATISTICAL METHODS OF ANALYSIS

6.1 General Principles

The statistical analyses will be performed by [REDACTED] with approval of the Sponsor, using SAS® Version 9.4 (or higher). All tables, figures and listings will be produced in landscape format.

In general, all data will be listed by subject and visit/time point where appropriate. The summary tables will be stratified by, or have columns corresponding to, treatment groups.

The total number of subjects in the treatment group (N) under the specified population will be displayed in the header of summary tables.

Data will be summarized using descriptive statistics for continuous variables. Unless otherwise specified, descriptive statistics will include number of subjects, mean, standard deviation, minimum, median, and maximum. Number of subjects with missing values will also be displayed, but only if non-zero. The minimum and maximum statistics will be presented to the same number of decimal places as the original data. The mean and median will be presented to one more decimal place than the original data. The standard deviation will be presented to two more decimal places than the original data.

In summary tables of categorical variables, counts and percentages will be displayed. The count [n] indicates the actual number of subjects in a particular category, which should always be less than or equal to the total number of subjects in the respective study group with known (non-missing) category [M]. Percentage will be obtained by: % = $n/M*100$. Unless otherwise specified, all percentages will be expressed to one decimal place.

All statistical tests will be two-sided at a significance level of $\alpha = 0.05$, unless otherwise indicated.

Baseline will be defined as the last assessment, scheduled or not, prior to the first dose of the study drug, unless otherwise specified. This notion of baseline will also be referred to as Part I baseline. Part II baseline will be defined as the last assessment, scheduled or not, prior to the first dose of the study drug in Part II. Part II baseline will be used in analysis of findings collected in Part II for subjects initially randomized to Placebo and re-randomized to SCD-044

(█ mg or █ mg) in Part II. Throughout this SAP, if the word “baseline” is used without qualification “Part I” or “Part II”, it will refer to Part I baseline.

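### Visual acuity is summarised as the Snellen denominator, which is not an interval scale, so its by-visit means can be dominated by one eye or hide worsening; logMAR would avoid this

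*SAP*

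**What the plan says.** SAP 6.12.8 schedules a complete ophthalmologic examination "At the study Visits 1, 9 and 17 (Screening and study Weeks 12 and 32", including "best corrected visual acuity (Snellen chart" and OCT. Its results "will be summarized descriptively by eye (left or right), visit and treatment group". The two results named are "Best corrected visual acuity (Snellen denominator" and OCT central fovea thickness.

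SAP 6.1 says what a descriptive summary of a continuous variable contains: "descriptive statistics will include number of subjects, mean, standard deviation, minimum, median, and maximum". Read together, the two sections produce a mean and standard deviation of Snellen denominators in each arm, for each eye, at each visit.

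The visible text of 6.12.8 fixes no numerator or test distance and converts acuity to no other scale. It plans no change from baseline and no count of subjects whose acuity worsens. By contrast, SAP 6.12.7 does plan changes from baseline for spirometry. SAP 6.12.8 also plans counts of macular edema and/or uveitis, by visit and across all visits, and a listing of all the eye data.

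**The concern.** Snellen acuity is a ratio. Equal steps of vision are equal multiples of the denominator, not equal additions to it, so an arithmetic mean gives poor eyes far more weight than good ones. Two consequences follow. One poor eye can set the level of an arm's mean. A small gain in a poor eye can also cancel a similar loss in several good eyes, so the by-visit means look stable when acuity has fallen.

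Ocular safety is a recognised issue for this drug. SAP 3.1 excludes subjects with a history of uveitis on account of adverse events known for the class, and Protocol 9.7 names ophthalmologic examinations among the safety assessments. Because no change from baseline is planned for acuity, a reader has to judge it by comparing means across visits, which is where the scale problem appears.

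**Working it through.** The documents state no figure for visual acuity, so there is nothing to reproduce. The check compares the planned variable with logMAR.

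**Inputs from the documents**
- Variable: Snellen denominator (SAP 6.12.8). Statistics: n, mean, SD, minimum, median, maximum (SAP 6.1).
- Arm sizes: "Approximately 240 subjects will be enrolled in the study" (Protocol 4.1), allocated 3:1:1:3 to placebo, low, intermediate and high dose (SAP 3.1). 240/8 = 30, so the arms are about 90, 30, 30 and 90.

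**Assumption:** the individual acuities below are illustrative. All are in 20-foot notation, so no example depends on mixed charts. Each n counts one eye per subject, because the table is by eye.

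**Formula:** logMAR = log10(denominator/numerator). A mean logMAR of m corresponds to a denominator of 20 × 10^m.

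**1. Unequal steps.** A doubling of the denominator is log10(2) = 0.301 logMAR wherever it starts, but the denominator changes by:

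| From | To | Change in denominator |
|---|---|---|
| 20/20 | 20/40 | 20 |
| 20/40 | 20/80 | 40 |
| 20/100 | 20/200 | 100 |
| 20/200 | 20/400 | 200 |

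**2. One poor eye.** One eye is at 20/400 (logMAR log10(20) = 1.301) and the rest at 20/20 (logMAR 0).
- n = 30: mean denominator (29 × 20 + 400)/30 = 32.7. Mean logMAR 1.301/30 = 0.0434, and 20 × 10^0.0434 = 22.1, about 20/22.
- n = 90: mean denominator (89 × 20 + 400)/90 = 24.2. Mean logMAR 1.301/90 = 0.0145, and 20 × 10^0.0145 = 20.7.

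In both cases the median is 20 and the maximum 400.

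**3. Hidden worsening (n = 30).** One eye improves from 20/200 to 20/100, five worsen from 20/20 to 20/40, and 24 stay at 20/20.
- Mean denominator before: (200 + 29 × 20)/30 = 26.0. After: (100 + 5 × 40 + 24 × 20)/30 = 26.0.
- Mean logMAR before: 1.000/30 = 0.033. After: (0.699 + 5 × 0.301)/30 = 0.074.
- SD before: √[(174² + 29 × 6²)/29] = √1080 = 32.9. After: √[(74² + 5 × 14² + 24 × 6²)/29] = √252.4 = 15.9.

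| Statistic | Before | After |
|---|---|---|
| Mean denominator | 26.0 | 26.0 |
| SD | 32.9 | 15.9 |
| Minimum | 20 | 20 |
| Median | 20 | 20 |
| Maximum | 200 | 100 |
| Mean logMAR | 0.033 | 0.074 |

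No planned statistic shows that five eyes lost 0.301 logMAR each. The falling maximum and SD, if anything, suggest improvement.

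**The case against.** The strongest reply is that the mean is one of six statistics and that little rests on it. In the one-poor-eye example the same row shows a median of 20 and a maximum of 400, so a careful reader sees the outlier. Only the low- and intermediate-dose arms have about 30 subjects; at 90 the distortion is much smaller. Ocular harm is also covered by OCT thickness, the macular edema and uveitis counts, the adverse-event tables and full listings. Protocol 9.7 plans no inferential safety analysis, and no visible rule uses mean acuity. All of this stands and limits the importance of the point. It does not answer the third example, where the median, range and SD also fail to show the worsening.

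A reader might go further and infer that foot and metre charts will be mixed, because the Protocol synopsis gives study starts "in North and Latin America: June 2021" and "in Europe: July 2023 [anticipated open for recruitment". If a share s of eyes at 20/20 were recorded as 6/6, the mean denominator would be 20(1 − s) + 6s, from 20 at s = 0 to 6 at s = 1. The documents do not support that inference. They name the regions but not the charts. The text of Protocol Section 5.7, cited for the eye examination, is not in the public version, and the eCRF and table shells are separate documents. Any of these may fix the numerator. Mixed notation is a possible further reason for the change, not a demonstrated fault.

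Nor do the documents support saying that the table will report a change where there is none. No change from baseline is planned for acuity. Mixed notation would shift the level, and would create a spurious trend only if notation switched within subjects or dropout differed by notation.

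**Conclusion.** The point holds as a minor one. The SAP names a poorly scaled variable, and its general rules put a mean and SD on it. With a single notation, that mean can be dominated by one eye (32.7 against about 20/22 in an arm of 30; 24.2 against 20/20.7 in an arm of 90) and can stay at 26.0 while mean logMAR worsens from 0.033 to 0.074. These sizes rest on illustrative acuities and approximate arm sizes; the unequal steps of the scale do not. The consequence is one descriptive safety row that is hard to interpret. No efficacy result, test or other ocular output is affected.

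**What to change.** In SAP 6.12.8, derive logMAR = log10(denominator/numerator) for each eye and summarise logMAR and its change from baseline by eye, visit and treatment group. For placebo subjects re-randomised in Part II, SAP 6.1 already prescribes the Part II baseline, which on the visit schedule would normally be the Week 12 examination; the section should say so. Add the number and percentage of subjects who worsen in either eye by a threshold that the sponsor specifies before unblinding; the documents supply no such threshold. Keep the recorded Snellen values in the listing.

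The cost is one derived variable and changes to SAP and shell wording, with no new assessment. This assumes that the numerator is recorded or fixed. The sponsor should confirm that from the eCRF, and state the notation in the SAP.

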7. TIMING OF ANALYSES

6.9.1.1 Once the last subject completes Week 16 visit (or early termination prior to Week 16), statistical analysis will be conducted on all available data to evaluate the Part I results including the primary and key secondary efficacy outcomes. At this time all planned tables, listing and figures pertaining to Part I of the study will be created. This will be the final analysis for the primary efficacy endpoint. Investigational sites, subjects, and study team members directly involved in study activities will remain blinded to study treatment assignments until the last subject completes the follow-up period. The Interim Blinding Maintenance and Communication Plan provides further details related to unblinding of personnel involved in reporting activities for the analysis of Part I. Sharing of subject-level unblinded information for the Part I analysis will be confined to a designated unblinded study team.

When all subjects complete the study, the final analysis will be performed. At this time the randomization code will be released and the statistical and programming team that was blinded throughout the study will become unblinded. For the final analysis all planned tables, listings and figures will be created.

8. CHANGES FROM PROTOCOL-SPECIFIED ANALYSES

Handling of intercurrent events is expanded in this SAP. There are no other changes from the protocol-specified analyses.

9. LIST OF PLANNED TABLES, FIGURES, AND LISTINGS

See separate document with the table, figure and listing shells.

